### 8.4 OBSERVATION PERIOD FOR ADVERSE EVENT REPORTING

The observation period for AE and SAE reporting for de novo subjects will start at the time of giving written informed consent for participation in the current study and finish 15 days after the last dose of study drug or the last visit, whichever is later. For subjects who participated in one of the core studies, the observation period for adverse events will start at Visit 1 of 1503 and finish 15 days after the last dose of study drug or the last visit, whichever is later. Ongoing AEs from the core studies will be considered medical history unless there is an increase in the frequency or severity of the condition from the core study.

If the investigator becomes aware of an SAE that has started after the observation period has finished, and the event could in some way be associated with IMP (irrespective of whether or not it is considered by the investigator to be causally related to IMP), then this must also be reported to the Sponsor (see Section 8.6).

## 8.5 ADVERSE EVENT REPORTING

### 8.5.1 Adverse Events

At each clinical evaluation, the investigator (or delegate) will determine whether any AEs have occurred. Adverse events will be recorded in the AE page of the CRF. If known, the medical diagnosis of an AE should be recorded in preference to the listing of individual signs and symptoms. The investigator must follow up on the course of an AE until resolution or stabilization. If an AE is ongoing after the end of study visit, the AE will continue to be followed up until resolution or stabilization.

If, during the study period, a subject presents with a pre-existing condition that was not noted at the time of study entry, the condition should be retrospectively recorded in the Medical History section of the CRF.

## 8.6 SERIOUS ADVERSE EVENTS REPORTING

This study will comply with all applicable regulatory requirements and adhere to the full requirements of ICH Topic E2A ([Clinical Safety Data Management: Definitions and Standards for Expedited Reporting \[1994\]](#)).

In the event of a SAE the investigator or delegate must:

1. Enter all relevant information in the AE page of the eCRF.
2. Inform the Medical Monitor or the Sponsor of the SAE via email or telephone within 24 hours of becoming aware of the SAE.
3. Follow the initial notification with a completed SAE report form. The SAE form must be emailed or faxed to Inventive Health Care within 24 hours of becoming aware of the SAE.

**All SAEs that occur during the course of the study, beginning the day Informed Consent is signed for de novo subjects and at Visit 1 for subjects from the core studies, whether or not causally related to IMP must be reported immediately via telephone or email (within 24 hours of the investigator becoming aware of the event) to the Sponsor or the Medical Monitor.**

Adverse events occurring in the period between the time the subject gave written informed consent and the first exposure to IMP that meet one or more of the seriousness criteria for AEs must be reported to the sponsor and the Medical Monitor in the same manner as other SAEs and will be included in the clinical study database.

Any SAE that occurs 15 days after the last dose of study drug or the last visit, whichever is later that is considered to be causally related to IMP must be **reported immediately (ie, within 24 hours of the investigator becoming aware of the event) to the Sponsor and the Medical Monitor.**

Contact details and guidance for reporting SAEs will be provided to study site before the study starts.

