### 8.3 CAUSALITY OF ADVERSE EVENTS

The causal relationship of an AE to IMP must always be assessed by the investigator. All AEs will be classified as either related or not related to IMP. If a causality assessment is not provided for an AE (including an SAE), that AE will be considered as related to IMP.

The degree of certainty with which an AE is attributed to IMP or an alternative cause (eg, natural history of the underlying disease, concomitant medication) will be determined by how well the event can be understood in terms of:

- Known pharmacology of ZX008
- Clinically and/or pathophysiologically plausible context
- Reaction of a similar nature previously observed with similar products, or reported in the literature for similar products as being product related (eg, headache, facial flushing, pallor)
- Plausibility supported by the temporal relationship (eg, the event being related by time to administration or termination of treatment with IMP drug withdrawal or reproduced on rechallenge)
- The following classifications should be used in categorization of relatedness:
  1. Not Related: Concomitant illness, accident or event with no reasonable association with study drug.
  2. Related: The event follows a reasonable temporal sequence from administration of study drug and is definitive pharmacologically; cannot to be attributed to concurrent disease or other factors or medications. A clinically reasonable response should be observed if the study drug is withdrawn or dose reduced.

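### Sections 8.4 and 8.6 set different conditions for reporting late SAEs that may be associated with IMP but that the investigator judges not related

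*Protocol*

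**What the plan says.** Section 8.4 closes the observation period for AEs and SAEs at the same point for de novo and core-study subjects: they "finish 15 days after the last dose of study drug or the last visit, whichever is later". It then covers an SAE that starts later and comes to the investigator's attention. Its condition is that "the event could in some way be associated with IMP". Once that is met, the duty applies "irrespective of whether or not it is considered by the investigator to be causally related to IMP". The report goes to the Sponsor, and the reader is pointed to Section 8.6. Section 8.4 gives no time limit of its own.

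Section 8.6 opens with three general steps for any SAE, including notification within 24 hours. It then requires on-study SAEs to be reported within 24 hours regardless of causality. Its late-SAE sentence is narrower. It starts from "Any SAE that occurs 15 days after the last dose of study drug or the last visit, whichever is later", and it then limits the duty with the words "that is considered to be causally related to IMP must be". Such events go to both the Sponsor and the Medical Monitor, no later than 24 hours after the investigator learns of them.

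Section 8.3 makes causality a two-way call: "All AEs will be classified as either related or not related to IMP". An AE with no causality assessment is counted as related.

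**The concern.** Section 8.4 says that the investigator's causality view does not decide whether a late SAE is reported, and it sends the reader to 8.6. The one sentence there about late SAEs makes that view the deciding condition. The contrast inside 8.6 strengthens the narrow reading: on-study SAEs are reportable regardless of causality, and the late sentence then brings in a causality requirement. A site could reasonably take this as a deliberate narrowing of the duty.

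Long-term safety is the primary objective (Section 2.1), and Section 1.2 records that fenfluramine products were withdrawn in the USA after reports of heart valve disease and pulmonary hypertension. Whether a late serious event with a possible drug association reaches the Sponsor should not depend on which section the site consulted.

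**Working it through.** No sample size, rate or error probability is involved, so the check is a comparison of the provisions.

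| Element | Section 8.4 | Section 8.6, late-SAE sentence |
|---|---|---|
| Cut-off | 15 days after last dose or last visit, whichever is later | Same |
| Condition | Possible association with IMP | Considered causally related to IMP |
| Investigator's causality view | Not a condition | The condition |
| Time limit | None stated; refers to 8.6 | 24 hours from awareness |
| Recipient | Sponsor | Sponsor and Medical Monitor |

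The cut-off match assumes that 8.6 means more than 15 days after the reference date. Its literal wording could be read as the 15th day itself, but that would leave the sentence with almost no purpose.

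Late SAEs can then be sorted by how each rule treats them:

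1. **Judged related, or causality missing.** A missing assessment counts as related under 8.3. These are reportable under both provisions.
2. **Possibly associated, but actively judged not related.** These are reportable under 8.4 and fall outside the late-SAE sentence of 8.6.
3. **No conceivable association with IMP.** Neither provision requires a report.

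The rules therefore disagree only in category 2.

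Category 2 need not be empty. To be called related under 8.3, an event needs a reasonable time sequence, must be pharmacologically definitive, and must not be attributable to concurrent disease or to other factors or medications. Section 5.6 requires every subject to take at least one other AED, and all have Dravet syndrome. A possible drug association can thus coexist with a formal classification of not related.

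No other section settles category 2. Section 8.6.1 refers to Section 8.9 for an ongoing AE that becomes serious after the observation period. That is a different case from an SAE that starts late, and 8.9 adds neither a causality condition nor a reporting deadline.

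**The case against.** The sections can be read together. On that reading 8.4 is the general duty, and the late sentence of 8.6 adds an explicit 24-hour rule for related events. Section 8.6 nowhere says that other late SAEs need not be reported. Its opening steps carry no causality condition, and the 8.4 cross-reference could be taken to lead there. This stands as far as it goes: the 8.4 obligation survives, and a reader who inferred that such events are excluded from reporting would be going beyond the text. It does not remove the mismatch. Even on the harmonised reading, category 2 has no time limit specific to late events, and the named recipients differ.

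A reader might also infer that capture of late valve disease or pulmonary hypertension turns on this sentence. The documents do not support that:

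- The window runs from the last visit if that is later than the last dose. Table 8 schedules ECHO and ECG at 3 and 6 months after more than 13 weeks of treatment, so a completed 6-month visit extends the window past that point.
- Section 8.9 follows subjects with signs of either condition on ECHO for at least 6 months from the last dose.
- Section 8.8 asks for pulmonary hypertension, and valvulopathy found outside study monitoring, to be reported within 72 hours even when not serious, with no causality condition.
- Subjects who move to commercial drug or Study 1900 have no post-dosing or cardiac visits here. Section 3.1, however, states that those on commercial drug will have follow-up ECHOs, and the others enter a further protocol.

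**Conclusion.** The inconsistency is real and minor. Sections 8.4 and 8.6 apply different conditions after the same cut-off, and the practical effect is confined to late SAEs that may be associated with IMP but have been actively judged not related. A site following the late-SAE sentence of 8.6 alone may leave these unreported. How often that would happen is a matter of site behaviour, on which the documents are silent.

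The number of affected events cannot be derived. A reader might turn to the interim counts in Section 1.3, where 80 of 330 subjects had a treatment-emergent SAE and 8 of 330 had one considered related, and compute 1 − 8/80 = 90% as the share a causality filter would remove. That figure should not be used. The counts come from the open-label treatment period, not from after the window. The 80 include 24 subjects with seizure, the condition under treatment. The proper denominator is late SAEs with a possible association, whereas the 80 may include events with none, which neither late-SAE provision requires to be reported.

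The conclusion rests on the wording alone and on reading the two cut-offs as the same.

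**What to change.** Reconcile 8.4 and 8.6 to one condition, one time limit and one set of recipients. The simplest route is to replace the late-SAE sentence in 8.6 with text to this effect: an SAE that starts after the observation period in 8.4 has ended, and for which an association with IMP is possible, is to be reported to both the Sponsor and the Medical Monitor within 24 hours of site awareness, however the investigator has classified causality. The recipients named in 8.4 should be aligned to match. Tying the sentence to the end of the observation period also removes the ambiguity about the 15th day.

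Narrowing 8.4 to related events would also end the contradiction, but it would give up the events that 8.4 expressly includes.

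The cost is one sentence in an amendment, the matching edit in 8.4, and a few more late SAE reports. No analysis, visit or treatment rule changes.

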### **8.6.1 Requirements for Immediate Reporting of Serious Adverse Events**

The minimum reporting requirements for immediate reporting of SAEs include:

1. Identifiable subject
2. Suspected drug product
3. Event description
4. Identifiable reporting source

In addition, the investigator must:

1. Report all SAEs to the relevant IRB/IEC within the timeframe specified by the IRB/IEC.
2. Submit follow-up reports to the Sponsor Global Clinical Safety and Pharmacovigilance and the Medical Monitor until the SAE has resolved, or, in the case of permanent impairment, until stabilized.
3. Ensure that the AE term(s) and causality assessment for all SAEs is entered in the CRF.

If the minimum requirements for reporting are fulfilled, the investigator should not wait to receive additional information to fully document the event before notifying the Sponsor.

When submitting SAE reports to the Sponsor, subjects should be identified only by their subject number and study number. The investigator should not include the subject's name and address.

SAE Update reports can be submitted to the Sponsor any time that additional relevant information becomes available. In cases of death, the investigator should supply the Sponsor and the IEC/IRB (as applicable, see Section 8.7) with any additional requested information as it becomes available (eg, autopsy reports and detailed medical reports). Once an SAE is reported to the Sponsor's Safety Group, a Safety Specialist may contact the investigator with follow-up questions.

The procedure to be followed if an ongoing AE becomes an SAE after the end of the observation period for AEs is described in Section 8.9.

## **8.7 REPORTING OF SERIOUS ADVERSE EVENTS BY INVESTIGATOR TO IEC/IRB**

The timeframe within an IEC/IRB must be notified of a death or an unexpected SAE considered at least possibly related to the IMP is stipulated by each individual IEC/IRB. The investigator is responsible for complying with the requirements for IEC/IRB notification. The investigator will notify the relevant IEC/IRB within the applicable timeframe by forwarding the safety report (eg, MedWatch/CIOMS form) completed by the Sponsor for the notifiable event.

## **8.8 REPORTING OF EVENTS OTHER THAN SERIOUS ADVERSE EVENTS BY INVESTIGATOR TO SPONSOR**

Even if none of the criteria for an SAE are fulfilled, any of the following events must be reported by the investigator to the Medical Monitor within 72 hours from the time the investigator is notified.

1. Hypersensitivity reactions
2. Pulmonary hypertension
3. Cardiac symptoms requiring intervention, or valvulopathy, if identified outside of study-related monitoring

## **8.9 FOLLOW-UP OF ADVERSE EVENTS**

Every effort should be made to follow-up subjects who continue to experience an AE or an SAE on completion of the study or until the AE resolves. All follow-up information (and attempted follow-up contacts) should be documented in the subject's medical records. Details of the subject's progress should also be submitted to the Sponsor's Global Clinical Safety and Pharmacovigilance and the Medical Monitor. In the event of a SAE, a blood sample for ZX008 and AED PK should be collected as soon as feasible.

Subjects who are discontinued from the study or complete the study and have been found to have any signs of valvulopathy or pulmonary hypertension on ECHO will be followed until the

condition has resolved or stabilized where no further changes are likely, for a minimum of 6 months from the last dose of study medication.

### 8.9.1 Follow-up of Echocardiogram Findings

All ECHOs will be evaluated by a central reader from BioMedical Systems, Inc. (BMS), in consultation with the IPCAB, if warranted. Findings related to pulmonary hypertension or valvulopathy on any of the four valves (aortic, mitral, pulmonary, tricuspid) will be reported to the investigator with grades of normal, trace, mild, moderate, or severe. If the ECHO result has progressed in severity since the last reading, then new oversight measures will be enacted as described below in Levels 1-3. Table 12 describes the severity of ECHO findings with the level of increasing oversight if the subject is to remain in the study.

**Table 12. Clinical Measures Enacted Upon Increasing Severity of ECHO Findings**

Severity	Valve			
	Aortic	Mitral	Pulmonary	Tricuspid
Trace	Level 1	Level 1	Level 1	Level 1
Mild (≤18 years)	Level 2	Level 1	Level 1	Level 1
Mild (>18 years)	Level 2	Level 1	Level 1	Level 1
Moderate	Level 3	Level 2	Level 2	Level 2
Severe	Level 3	Level 3	Level 3	Level 3

Level 1: Continue per protocol

Level 2:

1. If there is a desire to continue study medication:
  - a. The investigator will evaluate the efficacy to date based on study diaries and consult with the parent/guardian, and determine whether study treatment was associated with significant, meaningful benefit in number, severity and/or duration of seizures and/or on the impact on daily functioning.
  - b. The investigator will consider whether the subject has had reasonable trials (dose and duration) of other available anticonvulsants (eg, VPA, CLB, or topiramate), alone or in combination, and not maintained the level of seizure control achieved with study medication.
2. If the investigator feels consideration of continued treatment is warranted considering benefit and potential risk, and the parent/guardian feels strongly that the subject be maintained on the study medication when understanding the risks, the parent/guardian must sign a new consent which describes the additional risk and the subject should provide assent if appropriate.
  - a. If both of these conditions are not met, the subject is discontinued from treatment.

3. The investigator prepares a case history and rationale for continuation to be submitted to the IDSMC for review, including consideration of effects on seizures and comorbidities.
4. The Co-Chairs of the IPCAB are alerted to the request and prepare, after consultation with BMS, an evaluation of the cardiopulmonary risk and proposed monitoring plan if applicable, for submission to the IDSMC.
5. IDSMC will review the submission from the Investigator and the IPCAB and unblind the subject's core study treatment, if warranted.
6. IDSMC makes a determination of appropriate path, including the possible outcomes:
  - a. Discontinue study medication
  - b. Increase frequency of ECHO and ECG monitoring
  - c. Add additional ECG and/or ECHO measures to be monitored
  - d. Reduce the dose of study medication

Level 3:

1. The investigator will evaluate efficacy to date based on study diaries and consult with the parent/guardian, and determine whether the achieved benefit justifies the consideration of continuing study treatment by the IDSMC. MINIMAL efficacy criteria for IDSMC consideration:
  - a. Seizures must be more than 75% improved (number of convulsive seizures per 28 days) on treatment over baseline, and improvement must be consistent.
  - b. The number, type, duration, and distribution of seizures at baseline should be of a severity, which justifies the risks of cardiopulmonary complications, considering the subject's age and overall health.
  - c. Subject has had reasonable trials (dose and duration) of other available anticonvulsants (eg, VPA, CLB, topiramate), alone or in combination, and not maintained the level of seizure control achieved with study medication.
2. If the investigator feels consideration of continued treatment is warranted considering benefit and potential risks, and the parent/guardian feels strongly that the subject be maintained on the study medication when understanding the risks, the parent/guardian must sign a new consent, which describes the additional risks and the subject should provide assent if possible.
  - a. If both of these conditions are not met, the subject is discontinued from treatment.
3. The investigator prepares a case history and rationale for continuation to be submitted to the IDSMC for review, which includes effects of study medication on seizures and comorbidities related to DS.
4. The Co-Chairs of the IPCAB are alerted to the request, and in consultation with BMS prepare an evaluation of the risks and proposed monitoring plan if applicable for submission to the IDSMC.

5. IDSMC will review the submission from the Investigator and the IPCAB and unblind the subject's core study treatment, if warranted.
6. IDSMC makes a determination of appropriate path, including these possible outcomes:
  - a. Discontinue study medication
  - b. Increase frequency of ECHO and ECG monitoring
  - c. Add additional ECG and/or ECHO measures to be monitored
  - d. Reduce the dose of study medication

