  - a. Onset of seizures in the first year of life in an otherwise healthy infant.

- b. A history of seizures that are either generalized tonic-clonic or unilateral clonic or bilateral clonic, and are prolonged.
  - c. Initial development is normal.
  - d. History of normal brain MRI without cortical brain malformation.
  - e. Lack of alternative diagnosis.
  - f. Meets one of the following 3 confirmatory diagnostic criteria:
    - i. Emergence of another seizure type, including myoclonic, generalized tonic-clonic, tonic, atonic, absence and/or focal has developed after the first seizure type.
    - ii. Prolonged exposure to warm temperatures induces seizures and/or seizures are associated with fevers due to illness or vaccines, hot baths, high levels of activity and sudden temperature changes and/or seizures are induced by strong natural and/or fluorescent lighting, as well as certain visual patterns.
    - iii. Genetic test results consistent with a diagnosis of Dravet syndrome (pathogenic, likely pathogenic, variant of unknown significance, or inconclusive but unlikely to support an alternative diagnosis.)
  - g. Subject has been approved for study inclusion by the Epilepsy Study Consortium.
  - h. Subject does not have an exclusionary cardiovascular or cardiopulmonary abnormality based on ECHO, ECG or physical examination and is approved for entry by the central cardiac reader. Exclusionary abnormalities include, but are not limited to:
    - i. Mild or greater mitral or aortic valve regurgitation in subjects >18 yrs of age
    - ii. Possible signs of pulmonary hypertension with abnormal or greater than upper limit of normal values
    - iii. Evidence of diastolic dysfunction
  - i. Subject must have had  $\geq 4$  convulsive seizures (tonic, tonic-atonic, tonic-clonic, clonic) per 4-week period for past 12 weeks prior to screening, by parent/guardian report to investigator or investigator medical notes.
  - j. All medications or interventions for epilepsy (including ketogenic diet [KD] and vagal nerve stimulation [VNS]) must be stable for at least 4 weeks prior to screening and are expected to remain stable throughout the study.
11. Subject's parent/caregiver is willing and able to be compliant with diary completion, visit schedule and study drug accountability.

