#### **4.4 REMOVAL OF SUBJECTS FROM THERAPY OR ASSESSMENT**

While subjects are encouraged to complete all study evaluations, subjects may voluntarily withdraw from the study for any reason at any time. They may be considered withdrawn if they fail to return for visits, or become lost to follow-up for any other reason.

If premature withdrawal occurs for any reason, the investigator must make a genuine effort to determine the primary reason for a subject's premature withdrawal from the study and record this information on the CRF. All subjects who withdraw from the study with an ongoing AE must be followed until the event is resolved or deemed stable. If a subject withdraws prematurely after dosing, all data to be collected prior to discharge from the clinical site should be collected at the time of premature discontinuation or at the scheduled discharge.

For subjects who are lost to follow-up (ie, those subjects whose status is unclear because they failed to appear for study visits without stating an intention to withdraw), the investigator should show "due diligence" by documenting in the source documents the steps taken to contact the subject (eg, dates of telephone calls, registered letters).

Subjects must be discontinued from the study for the following reasons, if deemed appropriate by the Sponsor or investigator:

1. Development of signs or symptoms indicative of cardiac valvulopathy or regurgitation (mitral, aortic, tricuspid, pulmonary valves), or pulmonary hypertension for which IDSMC, in consultation with the IPCAB, the central cardiac reader, and the investigator believe the benefit of continued participation does not outweigh the risk.
2. Subject is found to have entered the clinical investigation in violation of the protocol.
3. Subject requires or starts using the use of an unacceptable or contraindicated concomitant medication.
4. Subject's condition changes after entering the clinical investigation so that the subject no longer meets the inclusion criteria or develops any of the exclusion criteria.
5. Subject is noncompliant with procedures set forth in the protocol in an ongoing or repeated manner.
6. Subject experiences an AE that warrants withdrawal from the clinical investigation.

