7. Clinically significant worsening of seizures, judged by investigator or subject/caregiver such that treatment outside of the protocol and other than ZX008 is assumed to be in the subject's best interest. Frequent or increased use of rescue medication may be considered indicative of worsening.
8. An "actual suicide attempt" as classified by the C-SSRS.
9. It is the investigator's opinion that it is not in the subject's best interest to continue in the study.

10. Subject is found to be pregnant while on study.

Discontinuation decisions will be made at each participating site by the site investigator, except that discontinuations due to development of cardiovascular or cardiopulmonary complications are to be made by the IDMSC with input from the IPCAB and the investigator.

If feasible, the process of discontinuation should be discussed with the Medical Monitor. The decisions regarding the discontinuation of the investigational therapy, whether the study medication should be stopped immediately or tapered should be discussed with the Medical Monitor, but final decisions about the process will remain at the discretion of the site principal investigator.

Subjects may withdraw their consent to participate in the study at any time without having to justify the reason for doing so. The decision to withdraw consent and discontinue participation in the study will not prejudice the subject's future medical treatment in any way. Subjects must be discontinued from receiving ZX008 and/or participating in any further study procedures under the following circumstances:

- The subject or the subject's legally authorized representative wishes to discontinue participation in the study
- The investigator advises that the subject's safety or well-being could be compromised by further participation in the study
- The Sponsor requests that a subject discontinues participation in the study (eg, due to suspicion of fraud, multiple enrollments in clinical studies, lack of compliance, etc)

The IDSMC may request that the study be terminated after review of the safety information at any time during the study. The IDSMC will review the data for the development of heart valve disease and pulmonary hypertension as they occur on a case-by-case basis and at regular meetings.

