**5. Alternative Dispensation for Study Drug Alternative Dispensation**

Shipments of investigational product may be sent by courier from site pharmacy to the subject's home via Sponsor-approved processes if the subject cannot or will not attend the dispensation visit(s). This shipment of drug should be arranged for patients who are due in the clinic for a drug dispensation visit. Other alternative dispensation, such as curbside pickup, may be implemented provided they are approved by the Sponsor and appropriate safeguards are taken to ensure compliance with existing regulatory requirements for maintaining investigational product accountability. Detailed instructions for drug handling, storage, accountability, etc. are described in the Pharmacy Manual.

8. Table 11 updated to Table 12. Table was amended to reflect the latest safety database, contained in the NDA and MAA and updated in the 120-day Safety update, the lack of appearance of valvular heart disease or PAH in any subject supports the removal of IDSMC oversight of mild mitral regurgitation in children. It further supports utilization of the Level 2 review for moderate mitral, pulmonic and tricuspid regurgitation in the absence of any indicators of PAH.

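### For a de novo adult who develops mild mitral regurgitation, Table 12 says continue while Section 4.4 item 4 with inclusion 10h(i) lists the same finding as a reason to discontinue, and Level 1 has no link to the IDSMC

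*Protocol*

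**What the plan says.** Five parts of the protocol bear on an on-study mitral finding in a de novo adult.

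- **Section 8.9.1 and Table 12.** All ECHOs are read centrally, and a finding that has progressed is assigned Level 1, 2 or 3. The section frames the levels this way: "Table 12 describes the severity of ECHO findings with the level of increasing oversight if the subject is to remain in the study". In the row for mild findings over age 18, aortic is Level 2 and mitral, pulmonary and tricuspid are Level 1. The text for Level 1 is complete in four words: "Level 1: Continue per protocol".
- **Section 4.1, inclusion 10h(i).** Among the exclusionary abnormalities it names "Mild or greater mitral or aortic valve regurgitation in subjects >18 yrs of age". Criterion 10 applies only to subjects aged >18 to ≤35 who were not in a core study.
- **Section 4.4, lead-in and item 4.** The list opens "Subjects must be discontinued from the study for the following reasons, if deemed appropriate by the Sponsor or investigator". Item 4 covers a change in condition after entry such that "the subject no longer meets the inclusion criteria or develops any of the exclusion criteria".
- **Section 4.4, item 1.** This is the item specific to valve regurgitation and pulmonary hypertension. It rests discontinuation on the IDSMC's view of benefit against risk, formed with the IPCAB, the central reader and the investigator.
- **Section 4.4, after the list.** Decisions generally belong to the site, but "discontinuations due to development of cardiovascular or cardiopulmonary complications are to be made by the IDMSC with input from the IPCAB and the investigator" (the committee's abbreviation is misspelled there).

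**The concern.** Take a 25-year-old de novo subject whose mitral reading moves from trace to mild. A site that opens Table 12 finds an instruction to carry on with nothing added. A site that opens Section 4.4 finds that the subject no longer satisfies criterion 10h(i), which is a listed reason to discontinue. It also finds that it is not the body that decides. Nothing in either section says which one prevails.

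Long-term safety is the primary objective, and Section 1.2 records that fenfluramine products left the US market after reports of heart valve disease. The handling of a new valve finding should not turn on which section a site consults first.

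**Working it through.** There is no sample size, power or error-rate figure to reproduce. The check is a comparison of the provisions plus one proportion.

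**Step 1: who is affected.** Section 3.2 allows up to about 340 core-study subjects and up to 50 de novo subjects. Criterion 10 binds only the latter, so the share exposed to the conflict is at most

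50 / (340 + 50) = 50 / 390 = 0.128, or 12.8%.

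Every de novo subject is over 18 at screening and so sits in the adult row of Table 12 from the first visit.

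**Step 2: the same finding under each provision.**

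| Provision | Mild mitral regurgitation in a de novo subject |
|---|---|
| Table 12, mild, >18 years | Level 1, continue; no further step |
| 4.4 item 4 with 10h(i) | Listed discontinuation reason, subject to sponsor or investigator judgement |
| 4.4 item 1 | Depends on the IDSMC's benefit-risk view |
| 4.4, text after the list | Cardiac discontinuation decided by the IDSMC |

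The words of Level 1 do not settle the matter. Continuing in line with the protocol includes continuing in line with Section 4.4, which contains item 4.

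**Step 3: does Level 1 reach the decision-maker?** The steps of preparing a case history, alerting the IPCAB co-chairs and submitting to the IDSMC appear only under Levels 2 and 3. Section 8.9.1 announces new oversight measures when a reading progresses, but Level 1 adds none. The 72-hour reporting rule in Section 8.8 covers valvulopathy found outside study monitoring, so a scheduled study ECHO does not trigger it.

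Other routes exist. Section 4.4 has the IDSMC look at emerging heart-valve data case by case and at its meetings, and Section 3.7.1 adds periodic review of ECHO data. Section 3.7.2 sends cases that meet a pre-defined threshold to the IPCAB, which advises the IDSMC. Level 1 refers to none of these. Whether mild mitral regurgitation meets the IPCAB threshold cannot be checked here: Section 7.3.8 places the ECHO thresholds in Table 10, and Table 10 as shown has no cardiac entry.

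**Step 4: the age split.** The two Mild rows, ≤18 and >18 years, both read Level 2, 1, 1, 1 across aortic, mitral, pulmonary and tricuspid. The split changes nothing. That is redundancy rather than contradiction, but it leaves the reader unsure whether the adult row was meant to differ.

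**Step 5: is the finding routine elsewhere in the protocol?** No. Appendix 11 caps an ECHO delay at 6 weeks once mitral regurgitation is mild or worse. It allows up to 3 months when mitral regurgitation is absent or trace, aortic regurgitation is absent and PASP is below 30 mmHg.

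**The case against.** The best defence is that these provisions can be read together. The Section 4.4 list is discretionary. Item 1 is the specific rule for regurgitation and could be taken to displace the general item 4. Criterion 10h is written as an entry gate, with approval by the central cardiac reader. Item 4 also cannot be applied literally: inclusion 4 requires that convulsive seizures are not fully controlled, so a literal reading would make complete seizure control a discontinuation reason. Finally, Table 12 speaks only of subjects who are staying in the study.

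Much of this stands, and it rules out a flat clash between a duty to continue and a duty to stop. It does not remove the ambiguity. Nothing says that item 1 overrides item 4. The discretion in the lead-in goes to the sponsor or investigator, whereas the later text gives cardiac discontinuations to the IDSMC. The condition in Section 8.9.1 presupposes a decision to keep the subject, and Level 1 routes that decision to nobody.

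A reader might also infer more than the documents support:

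- **That the conflict covers every subject over 18.** Core-study subjects who pass 18 are in the adult row but are not bound by 10h(i). Their rule is exclusion 3, which turns on judged clinical significance and sets no threshold at mild.
- **That the IDSMC never sees such a case.** Sections 4.4 and 3.7.1, and possibly 3.7.2, provide other routes. What is missing is a step or cross-reference in Level 1.
- **That the amendment rationale proves the adult row wrong.** Item 8 of the Summary of Protocol Amendment 5.0 says the data "supports the removal of IDSMC oversight of mild mitral regurgitation in children". That is change-log text, and it would fit equally well if the adult row had already been Level 1.
- **That follow-up after a finding would vary by site and alter the adult cardiac conclusions.** Table 8 and Section 8.9 fix follow-up after treatment stops, and Table 1 fixes the ECHO schedule on treatment. The protocol gives no incidence of mild mitral regurgitation in adults from which an effect on conclusions could be derived.

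**Conclusion.** The point holds in a narrow form. For de novo adults, Table 12 and Section 4.4 item 4 with 10h(i) point in different directions on new mild mitral regurgitation. The level assigned to the finding also lacks any stated path to the committee that Section 4.4 makes responsible. At most 50 of about 390 planned subjects (12.8%) could be affected. Few cases are likely: Section 1.3 reports that the abnormal-ECHO events among 330 enrolled subjects at the October 2019 cut-off were all trace regurgitation.

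The conclusion rests on two readings: that item 4 reaches criterion 10h(i) after entry, and that no document outside the protocol, such as the IPCAB manual or the IDSMC charter, already settles precedence. Even if one does, the protocol is what sites follow. This is a wording defect with a bearing on subject safety. It does not threaten the analysis, and no view is taken on which provision is clinically right.

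**What to change.** The IPCAB, the IDSMC and the sponsor should reconcile four texts: inclusion 10h(i), Section 4.4 items 1 and 4, the Section 4.4 sentence on who decides cardiac discontinuations, and the adult Mild row of Table 12. One sentence in Section 4.4 or 8.9.1 should then state which provision governs on-study ECHO findings in de novo adults and how the named decision-maker receives the case. The same revision should confirm whether the two Mild rows are meant to be identical. The content of the rule is for those bodies to decide.

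The cost is a few sentences in an amendment and some committee time. It needs no new data collection and no change to the analyses.
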